#### **9.4.2.2 Analysis Methods for Key Secondary Efficacy Variables**

##### **Proportion of participants who remain relapse-free up to Week 36**

The proportion of participants who remain relapse-free up to Week 36 will be analyzed as a binary response variable, where participants who remain relapse-free throughout the study up to Week 36 will be considered responders, but otherwise participants will be considered non-responders. Relapse is defined as the appearance of: 3 or more new lesions per month (blisters, eczematous lesions, or urticarial plaques); or at least one large ( $> 10$  cm diameter) eczematous lesion or urticarial plaques that do not heal within 1 week; or the extension of established lesions or daily pruritus in participants who have achieved disease control.

The estimand strategy is outlined in [Table 10](#) above. Intercurrent events of rescue use with OCS after having previously achieved disease control, restricted medication use, and study withdrawal are unfavorable outcomes and will be handled with a composite strategy whereby participants experiencing these events prior to Week 36 will be considered as non-responders (ie, not relapse-free) in the analysis. Likewise, participants with missing data at Week 36 for any other reason will be considered as not-relapse free.

For the primary analysis of the proportion of participants relapse-free at Week 36, a logistic regression model will be fitted using a logit link function. The model will include treatment, baseline disease severity (moderate or severe, with a BPDAI activity score of 56 points used as the threshold between moderate and severe) and time of BP diagnosis (ie, participants with newly diagnosed BP versus participants with a previous diagnosis of BP who have relapsed) as categorical covariates.

The model will be used to estimate the proportion who are relapse-free for benralizumab and placebo, the difference between these proportions (benralizumab – placebo), a rate ratio

(benralizumab/placebo), and an odds ratio, with corresponding 95% confidence limits. A p-value, corresponding to a 2-sided test, will be presented to compare the benralizumab and placebo treatment groups. Note that if the logistic regression model does not converge to a solution due to low response rates in certain categories, the endpoint will be analyzed using a Cochran–Mantel–Haenszel test.

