The primary endpoint is the proportion of participants who are in complete remission while off OCS for ≥ 2 months at Week 36.

A participant will be considered in complete remission for ≥ 2 months at Week 36 if a complete remission is recorded in the disease status eCRF at the clinical assessment which is assigned to the Week 36 visit when applying the windowing rules described previously, and a complete remission is recorded at least 55 days prior to this Week 36 date, and all evaluable disease states that are recorded during the 55 days between these assessments (ie, overall 8 weeks) are complete remission.

The disease state at each visit will be recorded on the eCRF form collecting the date of assessment and the disease state. A disease state clinical assessment reported in the eCRF as “Not Evaluable” will be considered as missing. Between two consecutive non-missing disease state assessments it will be assumed that the disease state collected at the first assessment is

current until the day before the second disease state assessment, unless intercurrent events happen. The same rule will be applied for two non-consecutive non-missing disease state assessments at windowed visits if at least one missing assessment is detected between them.

A participant will be considered off OCS for ≥ 2 months at Week 36 if off OCS on the day of the clinical assessment which is assigned to the Week 36 visit when applying the windowing rules and on the 55 days (ie, overall 8 weeks) before that date. Further details on the definition of day off OCS are contained in Section [3.1.5.1](#).

A participant will be considered in complete remission while off OCS for ≥ 2 months at Week 36 if both the definitions above are met.

Note that regardless of prior OCS use, participants who have been in complete remission while off OCS for ≥ 2 months at Week 36 will be classed as responders. For example, if participants require an increase in OCS dose after previously achieving disease control but they still taper and achieve the remission criteria by Week 36, this will be counted as response in the analysis. It is considered unlikely that this situation would emerge often, but given the clinical relevance of still being able to achieve remission and that OCS use is built into the remission definition, it is considered appropriate to count this situation as response in the analysis.

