Intercurrent events for this estimand are unfavorable outcomes and will be handled with a composite strategy. The set of intercurrent events consists of participants who receive medications deemed to be intercurrent events as per Section [3.1.5.2](#) and participants who withdraw from the study. The primary estimand will regard these participants as non-responders from the time such events occur up to Week 36.

Participants who withdraw from the study will be considered non-responders starting after the last available non-missing BP disease state clinical assessment.

Participants who receive medications deemed to be intercurrent events as per Section [3.1.5.2](#) will be considered non-responders starting from the date of start of restricted medications. Missing/partial start dates are not allowed for restricted medications.

Participants with missing data at Week 36 for any other reason will be considered as non-responders.

The amount of missing data for this study is expected to be low, as participants who prematurely discontinue IP will be asked to come in for all visits and complete all study assessments up to the end of the study.

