3.3 Key secondary efficacy outcome variables

3.3.1 Proportion of participants who remain relapse-free up to Week 36

The proportion of participants who remain relapse-free up to Week 36 will be analyzed as a binary response variable, where participants who remain relapse-free throughout the study up to Week 36 will be considered responders, but otherwise participants will be considered non-responders.

Relapse is defined as the appearance of: 3 or more new lesions per month (blisters, eczematous lesions, or urticarial plaques); or at least one large (> 10 cm diameter) eczematous lesion or urticarial plaques that do not heal within 1 week; or the extension of established lesions or daily pruritus in participants who have achieved disease control.

Details regarding collection of BP disease state clinical assessments and handling of missing data have been reported in Section [3.2](#).

Participants who need to increase their OCS dose as a rescue therapy to treat their BP after having previously achieved disease control, those who receive medications deemed to be intercurrent events as per Section [3.1.5.2](#), and those who withdraw from the study will be considered as not being relapse free up to week 36 (i.e. non responders in the analysis).

A supportive analysis of the time to first BP relapse will also be performed in order to explore the timing of relapse events.

The time (weeks) from randomization to the first BP relapse is defined as follows:

$$(date \text{ of } first \text{ relapse} - date \text{ of } randomization + 1) / 7$$

Participants who receive medications deemed to be intercurrent events as per Section [3.1.5.2](#) will be considered with a relapse on the date of start of restricted medications.

Participants who need to increase their OCS dose as a rescue therapy to treat their BP after having previously achieved disease control will be considered with a relapse on the date of OCS dose increase recorded with start date $>$ date of disease control assessment.

For restricted medications/OCS during the study missing/partial start dates are not allowed.

Participants who withdraw from the study or are lost to follow-up before the Week 36 assessment and don't have a relapse or a change in medications as described above will be considered as not-relapse free the day after their last available assessment showing them to be relapse-free.

Participants with missing data for any other reason will be considered as not-relapse free.

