The time from randomization to the first BP relapse for participants who do not experience any relapse will be censored at their last available assessment showing them to be relapse-free. The same intercurrent events as detailed above in this section will be applied.

All the data in the double-blind period will be included.

3.3.2 Cumulative OCS exposure (mg/kg) from baseline to Week 36 and from baseline to Week 16

Details about OCS usage will be collected at each scheduled visit by the Investigator as reported in Section [3.1.5.1](#).

Cumulative OCS exposure (mg/kg) from baseline to Week 36 and from baseline to Week 16 will be calculated for each participant over 4 weekly intervals.

For each visit from Visit 4 (Week 4) until Visit 13 (Week 36), excluding Visit 5 (Week 6), the OCS exposure (mg/kg) will be computed by summing the recorded doses taken during each day over the past 28 days, thus the day of the visit will not be included. It will be calculated using the 28 days prior to the day of the scheduled visit. No visit window will be applied to the scheduled visit day.

For Visit 13 (Week 36), if the 4 weekly interval based on the scheduled visit day is including any days after the actual Visit 13 (Week 36) day (ie, days in the OLE period) the 4 weekly OCS exposure will be computed by summing the recorded doses taken during only the days during the double-blind period and rescaling them into a 4 weekly interval. For example, if the Visit 13 (Week 36) 4 weekly interval includes only 25 days in the double-blind period, it will be computed by summing the recorded doses taken during these 25 days, dividing by 25 and multiplying per 28. If less than 14 days are in the double-blind period, the Visit 13 (Week 36) 4 weekly interval will be considered with missing data of OCS exposure.

More details on OCS daily exposure are reported in Section [3.1.5.1](#).

To compute the dose in mg/kg for each day of OCS assumption the baseline weight will be considered.

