6 CHANGES OF ANALYSIS FROM PROTOCOL

Section 2.1.5 OLE analysis set has been added to identify all participants who enter into the OLE period.

In Section 3.1.5.2 further detail around which restricted medications are considered intercurrent events has been provided.

In Section 3.2 the missing data handling strategy for the primary endpoint has been detailed to cover occurrences of missing disease state assessments between two non-missing assessments. This is to integrate and not to change the approach specified in the CSP that states: “Any participant with missing data at a specific time point will be considered as a non-responder at that time point.” This statement in the CSP is meant to be applied to any missing disease state assessment after the last non-missing assessment.

In Section 4.2.7.3 the ANCOVA model specified for the analysis of the change from baseline at Week 36 in BPDAI activity score has been changed removing baseline disease severity as categorical covariate. This categorical variable is derived based on the baseline BPDAI activity score which is already included in the model as continuous covariate.

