8.1.4 Tipping point analyses

To examine the impact of missing data, including the impact of non-responder/not relapse free imputations due to study withdrawal, for the primary and first key secondary endpoint respectively, tipping point analyses may be performed. These analyses will systematically vary the assumptions about outcomes among the subsets of participants on the treatment arms who withdraw from the study early or have missing data at Week 36 for any other reason.

Tipping point analyses are intended to identify the point at which the results would tip from statistically significant to not statistically significant. Thus, the tipping point analyses will only be performed if an endpoint achieves a nominally statistically significant result (ie, nominal p-value < 0.05).

The analyses will be performed following below steps:

- The proportions of participants non-responder/not relapse free will be analysed using a Pearson's chi-squared test, thus the stratification factors that are used in the main analysis will be disregarded. Since the strata will be balanced in respect of treatment assignment by virtue of the stratified randomisation scheme used, the only impact of this simplification should be that the inferences from the unstratified analysis will be somewhat conservative.
- For the primary analysis, participants who withdraw from the study early or have missing data at Week 36 for any other reason are by definition imputed as non-responders. For this sensitivity analysis, these participants will be altered from non-responder to responder in an iterative manner.
- At each step of the analysis one of these participants switches from not being responder to being responder, and the Pearson's chi-squared test is re-run. The results (statistical significance) are presented in a grid where the x-axis and the y-axis represent the number of participants assumed to be responder for placebo and benralizumab, respectively. The region where the conclusion changes, will be considered as the tipping point.
- The grid will be divided in 3 regions, limited in the top by the expected number of participants with missing values in the benralizumab treatment group which would have been responder if observed at Week 36 (based on the proportion of responders in participants who did not withdraw from the study early or have missing data at Week 36 for any other reason in the benralizumab treatment group):

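### SAP 3.3.1 drops the protocol's Week 36 limit from the missing-data failure rule for the second gated endpoint, which conflicts with the protocol and with the SAP 3.2 bridging rule that 3.3.1 cites

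*SAP*

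**What the plan says.** Protocol 9.4.2.2, for this endpoint: "participants with missing data at Week 36 for any other reason will be considered as not-relapse free".

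SAP 3.3.1, for the same endpoint: "Participants with missing data for any other reason will be considered as not-relapse free". No time point is given. The sentence comes after the definition of time to first relapse, among the rules that date events for that supportive analysis.

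Earlier in the same section, SAP 3.3.1 refers elsewhere for missing data: "Details regarding collection of BP disease state clinical assessments and handling of missing data have been reported in Section" 3.2. Section 3.2 holds two relevant rules:

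- A recorded disease state is carried forward until the next recorded one. This is also "applied for two non-consecutive non-missing disease state assessments at windowed visits if at least one missing assessment is detected between them".
- For the primary endpoint the Week 36 limit is kept: "Participants with missing data at Week 36 for any other reason will be considered as non-responders".

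For time to first relapse, SAP 3.3.1 makes withdrawal or loss to follow-up an event on the day after the last relapse-free assessment. Participants with no relapse "will be censored at their last available assessment showing them to be relapse-free", with the section's intercurrent events still applied.

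SAP Section 1 says that changes from the protocol are described in Section 6. Section 6 lists none for this endpoint.

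**The concern.** The protocol and the SAP state different failure rules for the same gated endpoint, and the difference is not declared. SAP 3.3.1 also points to a bridging rule that gives the opposite answer to its own closing sentence when an interim visit is missed. Nothing says which prevails, so the choice could be made in programming.

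The endpoint is test 2 of six (SAP 4.1.1). If it fails, cumulative OCS exposure and both BPDAI endpoints are not formally tested. SAP 3.4.5 gives the Week 16 relapse-free endpoint the same derivation rules, so the ambiguity carries over to it.

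There is also a smaller gap. A participant who stays in the study but has no Week 36 state is labelled not relapse-free with no event date, while the next paragraph censors participants who have no relapse.

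**Working it through.** **Side by side.** Three participants, none with rescue OCS, restricted medication or a recorded relapse:

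| Participant | Protocol 9.4.2.2 | SAP 3.2 rules cited by 3.3.1 | SAP 3.3.1 sentence, literal | Time to first relapse (SAP 3.3.1) |
|---|---|---|---|---|
| A: misses Week 20, attends Week 36 | Relapse-free | Relapse-free (gap bridged) | Not relapse-free | Sentence gives no event date; next paragraph censors |
| B: in study, no Week 36 state | Not relapse-free | Not relapse-free | Not relapse-free | Sentence gives no event date; next paragraph censors |
| C: withdraws after Week 20 | Not relapse-free | Not relapse-free | Covered by the withdrawal rule | Event, day after last relapse-free assessment |

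The binary rules disagree only for A. Once A's gap is bridged, the time-to-event question for A disappears too. The gap left in the supportive analysis is B. C has no conflict.

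**The plan's own figure.** The SAP gives no power for this endpoint. Its 85% (SAP 1.3) is for the primary endpoint at 50% versus 20%, 50 per arm, two-sided 5%. Fisher's exact test gives 85.3%, so that figure reproduces, and this point does not affect it.

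**Illustration of the literal reading on the binary test.**

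- From the documents: 10 scheduled visits between baseline and Week 36 (Weeks 2, 4, 6, 8, 12, 16, 20, 24, 28, 32; SAP Table 2); 50 per arm; two-sided 5%.
- Assumed: a miss rate m per visit, independent across visits and equal in both arms; relapse-free rates of 60% and 30%.
- Share missing at least one interim visit: f = 1 − (1 − m)^10. Each relapse-free rate is multiplied by (1 − f), and power is for the chi-squared test by exact enumeration.

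| m | f | Rates after scoring | Power |
|---|---|---|---|
| 0 | 0 | 60% vs 30% | 87.6% |
| 0.5% | 4.9% | 57.1% vs 28.5% | 84% |
| 1% | 9.6% | 54.3% vs 27.1% | 81% |
| 2% | 18.3% | 49.0% vs 24.5% | 73% |
| 3% | 26.3% | 44.2% vs 22.1% | 66% |

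For m = 2%: 0.98^10 = 0.817, so f = 0.183, and 0.60 × 0.817 = 0.490 against 0.30 × 0.817 = 0.245.

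**Second set of assumptions.** This takes 33% on placebo (the placebo relapse-free rate SAP 1.3 cites from the mepolizumab trial), an assumed 30-point gain to 63%, all 11 visits including Week 36, and the normal approximation. Power with nothing missing is 86.3%. At m = 2%, the Week 36 rule affects 2% of participants and gives 84.9%. The literal reading affects 1 − 0.98^11 = 19.9% and gives 70.0%.

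**The case against.** The strongest reply is that the section as a whole does not say what the sentence says alone.

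- The reference to SAP 3.2 brings in both the bridging rule and a Week 36 limit.
- The tipping-point text (SAP 4.2.7.5 and 8.1.4), which covers this endpoint, defines its set as those "who withdraw from the study early or have missing data at Week 36 for any other reason".
- Appendix 8.1.2 analyses the endpoint under the same assumption as the primary.
- Section 6 comments on the protocol's general missing-data statement: "This statement in the CSP is meant to be applied to any missing disease state assessment after the last non-missing assessment". That comment is written for the primary endpoint, but it explains the rules that 3.3.1 borrows.
- The disputed sentence follows a rule for those who leave before the Week 36 assessment and may only continue it. Given where it sits, it may not govern the binary test at all.

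Most of this stands. A reader might infer that the SAP has made any missed assessment a failure on a gated test. The documents do not support that, because the weight of the other text favours the Week 36 reading. What remains is a specific sentence, in the endpoint's own section, that contradicts the protocol, with nothing to say that the cross-reference overrides it.

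A reader might also infer that the section both counts and censors participants with missing data in general. It does not: withdrawals and losses to follow-up are dated events, and the listed intercurrent events override censoring. Failure in the binary analysis with censoring in a supportive one is not in itself a contradiction. The residual gap is participant B. That group should be small, since the Week 36 window opens at Day 238, can run to Day 280, and accepts unscheduled and discontinuation assessments.

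The power figures are open to challenge. Clustered misses would affect fewer participants than independent ones at the same rate. Some who miss visits go on to withdraw and fail anyway. A missed visit need not leave an empty analysis window. Each of these makes the illustration an overstatement.

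**Conclusion.** The concern holds as a conflict of wording on the second gated endpoint. SAP 3.3.1 omits the protocol's Week 36 limit without declaring it and contradicts the bridging rule it cites. It is not a settled change of rule, because other SAP text points to the Week 36 reading. It should be corrected, since programming the sentence literally would score an administrative missed visit as a relapse.

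No stated figure changes. A power loss arises only if the sentence is applied literally to the binary test. The fall from about 88% to 73% at a 2% miss rate depends on assumed relapse-free rates and assumed independent misses. The documents supply neither, and they expect missing data to be low, so the fall should not be read as an expected loss.

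For time to first relapse, the defect is limited to a non-withdrawn participant with no Week 36 state. That analysis is supportive and outside the hierarchy.

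**What to change.** 1. In SAP 3.3.1, restore the protocol's limit: a participant with no disease state at Week 36 for any other reason is not relapse-free. Add that a gap between two non-missing assessments is handled as in Section 3.2, and state that both rules apply to the binary endpoint.
2. In SAP 3.4.5, say that the same rules apply with Week 16 as the time point.
3. For time to first relapse, state one rule for a non-withdrawn participant with no Week 36 state: either an event on the day after the last relapse-free assessment, as for withdrawals, or censoring at that assessment. Either is defensible, but it must be fixed before unblinding.

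If the unlimited rule was in fact intended, it should be listed in Section 6 with a reason. The cost is a few SAP sentences, with no change to data collection, sample size or the testing order.

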### **8.3.2 Follow-up of AEs and SAEs**

After the initial AE/SAE report, the Investigator is required to proactively follow each participant at subsequent visits/contacts. All AEs will be followed until resolution, stabilization, the event is otherwise explained, or the participant is lost to follow-up.

Any AEs that are unresolved at the end of the study (final DBL) will be followed-up by the Investigator for as long as medically indicated, but without further recording in the eCRF. AstraZeneca retains the right to request additional information for any participant with ongoing AE(s)/SAE(s) at the end of the study, if judged necessary.

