3.1.5.1 OCS usage

During the double-blind period, participants will be treated with IP and OCS until BP disease control is achieved (Figure [1](#)), as detailed in the CSP Section 6.5.

During the OLE period, participants can receive corticosteroids (topical and/or oral) for BP relapse at the Investigator’s discretion, with the goal of tapering off the steroids to benralizumab monotherapy as soon as clinically indicated.

The participants will be asked to report daily the dosage of OCS taken over the past 24 hours on a provisioned handheld device at home. Details about OCS usage will then be collected at each scheduled visit by the Investigator. Only data collected in the electronic case report form (eCRF) will be included in the main OCS analysis.

A participant will be considered on OCS on a date if that date is included in the interval

OCS start date \leq date \leq OCS end date

Only OCS collected in the OCS eCRF form with dose > 0 will be considered. For any of the OCS with missing dose, the dose will be assumed to be the same of the latest of the previous OCS doses with dose > 0 . If end date is missing the OCS will be considered ongoing and the participant assumed to be on OCS until last contact for the participant.

Partial/missing dates for OCS during the study (apart from end date for ongoing OCS) are not allowed.

Any increase in OCS dose after BP disease control is achieved will be considered as OCS rescue use.

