3.1.6 Last contact

Last contact with the participant is defined as the latest of the below dates of assessments:

- Date of visits (on-site or home visits, remote audio or telephone visits)
- Date of randomization
- Start and end dates of dosing
- Date of disease state and BPDAI assessment
- Date of collection of laboratory evaluations
- Date of vital sign testing
- Date of physical examinations
- Date of ECGs
- Start and end dates of concomitant medications
- Start and end dates of hospitalization
- Start and end dates of AE

Dates of contact with the participant or dates of completion/discontinuation are not included. However, if at least one assessment among the ones reported above has occurred on the same date, the date of contact or completion/discontinuation will be indirectly included.

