The set of intercurrent events for this estimand consists of participants who receive medications deemed to be intercurrent events as per Section [3.1.5.2](#) and participants who withdraw from the study. These events will be handled with an effectiveness strategy, including all available data in a Mixed-effect Model for Repeated Measures (MMRM) until the occurrence of such events. This avoids making potentially implausible imputation assumptions around future OCS use that a composite strategy would involve. For example, for a participant who discontinues at a high daily OCS dose early in the study, imputing a high daily OCS dose for the remainder of the treatment period would result in an imputed

cumulative OCS dose higher than participants would ever realistically receive. Likewise, using a treatment policy strategy is also not considered appropriate, as the use of restricted medications would confound future OCS use. For example, if OCS were discontinued to receive another treatment due to lack of response or intolerance to OCS, the treatment policy approach would show a low cumulative OCS dose, which is a positive outcome and does not fairly represent the overall picture.

Participants who receive medications deemed to be intercurrent events as per Section 3.1.5.2 will be considered with missing OCS exposure (mg/kg) from the date of start of restricted medications. Hence for the 4 weekly interval that includes this date, the OCS exposure will be computed by summing the recorded doses taken during only the days before the start of the restricted medications and rescaling them into a 4 weekly interval. For restricted medications during the study missing/partial start dates are not allowed.

Participants who withdraw from the study will be considered with missing OCS exposure (mg/kg) starting from the last contact with the participant. Hence the 4 weekly interval that includes this, the OCS exposure will be computed by summing the recorded doses taken during only the days before the last contact and rescaling them into a 4 weekly interval.

Note that the list of intercurrent events does not include increases in OCS dose after achieving disease control, and all doses of OCS will be included in the derivation of cumulative OCS exposure from baseline to Week 36/Week 16.

3.3.2.1 Cumulative actual OCS exposure (mg) from baseline to Week 36 and from baseline to Week 16

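### For some withdrawn participants the SAP counts OCS exposure up to a last-contact date that can fall after both withdrawal and the last recorded OCS use

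*SAP*

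**What the plan says.** Cumulative OCS exposure to Week 36 and to Week 16 are tests 3 and 6 of the hierarchy (SAP 4.1.1). Both come from one MMRM on 4-week exposures (SAP 4.2.7.2). Four rules decide what a withdrawn participant contributes.

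- **Cut-off (SAP 3.3.2).** "Participants who withdraw from the study will be considered with missing OCS exposure (mg/kg) starting from the last contact with the participant". The interval containing that date is summed over the days before it and rescaled to 28 days.
- **Definition (SAP 3.1.6).** "Last contact with the participant is defined as the latest of the below dates of assessments". The list includes "Start and end dates of concomitant medications", "Start and end dates of hospitalization" and "Start and end dates of AE". It adds: "Dates of contact with the participant or dates of completion/discontinuation are not included".
- **Open OCS records (SAP 3.1.5.1).** A missing end date is allowed for ongoing OCS. The record is then treated as continuing, with "the participant assumed to be on OCS until last contact for the participant".
- **Estimand (SAP Table 8; Protocol Table 10).** For study withdrawal, OCS dosing counts until the event occurs.

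Two other provisions bear on this. SAP 2.1 limits data to the date of study termination, but only for participants who withdraw consent. Protocol 8.3.2 says: "All AEs will be followed until resolution, stabilization, the event is otherwise explained, or the participant is lost to follow-up".

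**The concern.** The date that ends OCS exposure need not be one on which anybody asked about OCS. An AE end date or a hospital discharge learned after withdrawal moves the cut-off later, and an open OCS record fills the gap at its last dose. Those days are then treated as data.

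That departs from Table 8. It also differs from how SAP 3.3.2 treats restricted medication, where exposure is cut at the date of the event itself. It reintroduces, over a limited span, the carrying forward of a high dose that 3.3.2 sets out to avoid.

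The added amount depends on how long an AE, a hospital stay or a co-medication lasted, not on OCS use. The MNAR analysis in SAP 8.1.5 imputes missing intervals, so intervals already filled this way would not be varied by it.

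**Working it through.** The documents give no SD, expected effect, dropout rate or power for cumulative OCS exposure. There is no stated figure to reproduce, so the check applies the SAP rule to an example.

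**Inputs from the documents**
- Interval *k* covers study days 28(*k*−1)+1 to 28*k*: the 28 days before each scheduled visit (SAP 3.3.2), with randomization as Day 1 (SAP 3.1.4).
- Target dose: 0.5 mg/kg/day (Protocol 6.5.1).
- Taper: 20% per week down to 10 mg/day, then 2.5 mg every other week (Protocol 6.5.1).
- About 50 participants per arm (SAP 1.3).

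**Assumed for illustration**
- Withdrawal on day 60, not by withdrawal of consent; OCS record open at 0.5 mg/kg/day; AE end date day 110.
- Reference taper starting after the dose was held for 4 to 8 weeks, body weight 50 to 90 kg.

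**Formula.** Interval exposure = (sum of daily doses on days before the cut-off ÷ number of those days) × 28.

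**Step 1: the rule with two cut-offs**

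| Interval (days) | Cut at day 60 | Cut at day 110 |
|---|---|---|
| 1–28 | 14 | 14 |
| 29–56 | 14 | 14 |
| 57–84 | 3 days: 1.5 ÷ 3 × 28 = 14 | 28 days: 14 |
| 85–112 | missing | 25 days: 12.5 ÷ 25 × 28 = 14 |

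Because of the rescaling, days 57–84 come to 14 mg/kg either way. One extra interval of 14 mg/kg enters as observed.

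**Step 2: what the interval might otherwise have held.** A missing interval is not zero in an MMRM, so the protocol taper serves as a rough reference for days 85–112.
- 70 kg, dose held 4 weeks: 7 days at 7.5 mg, 14 at 5 mg and 7 at 2.5 mg = 52.5 + 70 + 17.5 = 140 mg; 140 ÷ 70 = 2.0 mg/kg.
- 50 kg, dose held 8 weeks: 14 days at 10 mg and 14 at 7.5 mg = 140 + 105 = 245 mg; 245 ÷ 50 = 4.9 mg/kg.

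Over the assumed weights and hold times the range is about 2 to 5 mg/kg. The excess is about 14 − 5 = 9 to 14 − 2 = 12 mg/kg. Divided by 50, that is 0.18 to 0.24, or about 0.2 mg/kg on the simple arm mean per affected participant.

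**Step 3: OCS last recorded by day 57.** If exposure ended there, days 57–84 and 85–112 would both be missing. With last contact on day 110 both are 14, a total of 28 mg/kg.
- 70 kg, held 4 weeks: the taper gives 3.9 + 2.0 = 5.9; 28 − 5.9 = 22.1; 22.1 ÷ 50 = 0.44.
- 50 kg, held 8 weeks: the taper gives 8.3 + 4.9 = 13.2; 28 − 13.2 = 14.8; 14.8 ÷ 50 = 0.30.

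The shift is about 0.3 to 0.45 mg/kg. For scale, a whole 36 weeks on the same taper totals about 28 to 43 mg/kg.

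**Step 4: no minimum on the partial interval.** With last contact on day 58, one day (day 57) becomes 0.5 × 28 = 14 mg/kg. The 14-day minimum in 3.3.2 is stated for Visit 13 only. The SAP's own Visit 13 example has a factor of 28 ÷ 25 = 1.12; here it is 28.

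**The case against.** The strongest reply is that the harmful case is narrow.
- Withdrawal of consent is already capped by SAP 2.1. For participants lost to follow-up, AE follow-up stops, and after death no clinical date should run on. What remains is mainly investigator-initiated or other withdrawals, and Protocol 7.2 expects withdrawal to be uncommon.
- Later contacts usually collect OCS as well. Protocol 7.2 asks for the IPD and follow-up visits where possible, Protocol 7.1.1.1 has telephone contacts that collect concomitant medications, and Protocol 6.5 requires dose changes to be recorded. Harm needs a site that learns an AE end date but not OCS status.
- SAP 4.2.7.2 expects little missing data.

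All of this limits frequency and stands. It does not supply a cap where the rule has none.

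Three stronger readings are tempting but not supported.
- A reader might infer that this is exactly the carry-forward 3.3.2 rejects. That passage rejects holding a high dose for the rest of the treatment period; here it stops at last contact.
- A reader might multiply raw days: 50 × 0.5 = 25 mg/kg, or 0.5 mg/kg on the arm mean. This ignores the rescaling, which already fills days 57–84, and treats missing as zero.
- A reader might infer that closed OCS records produce false zeros. Nothing says sites close records administratively at withdrawal; a recorded end date is meant to be a real stop, for which zero is right.

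**Conclusion.** The point holds as a wording fault with a small effect. Followed literally, SAP 3.3.2, 3.1.6 and 3.1.5.1 can place unrecorded OCS doses in the MMRM for participants who leave other than by withdrawing consent, contrary to Table 8.

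The size is about 0.2 mg/kg on a 50-person arm mean per affected participant when one interval differs, and about 0.3 to 0.45 when two do. This rests on an open record at 0.5 mg/kg/day, the assumed dates, and the protocol taper as the reference. The amounts scale with dose: a full interval is 7 mg/kg at 0.25 mg/kg/day and 21 at 0.75. A model prediction conditional on a high earlier dose would make the excess smaller.

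Test 6 is directly affected only through intervals up to Week 16. The number of participants affected, any imbalance between arms and the effect on either test result cannot be derived from the documents, so no claim of a biased treatment comparison is made. Priority is low, but the correction is cheap.

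**What to change.** In SAP 3.3.2, and in the open-record rule of 3.1.5.1 for withdrawn participants only:
1. End OCS exposure at the earlier of the study withdrawal date and the last date for which OCS use was recorded in the eCRF, from any source (visit, telephone, relative or medical records).
2. Set later days to missing.
3. Apply the existing 14-day minimum to every rescaled partial interval, not only Visit 13.

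Keep 3.1.6 unchanged for its other uses. In the example, days 57–84 would then hold at most 3 usable days and become missing, as would days 85–112.

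The cost is a short SAP edit and a changed cut-off in the derivation, to be made before unblinding. No new data are needed. The downside is slightly shorter OCS follow-up for a few withdrawn participants.
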